The algorithm will push data up to a cloud server that can be monitored remotely every 5 minutes. A study coordinator will be present once the closed loop study begins to run the YSI analyzer with the ability to monitor the APC remotely via a cloud system on the web in the event of any issues. This will allow study staff to give immediate assistance with any difficulties using the APC controller. The APC will generate alerts on the smartphone according to Appendix M. The subjects will all be trained as to the action required by each alert. Each alert has a specific condition to be met for it to be considered serviced (i. e. enter treatment with oral carbohydrates). The refractory period is also specific to each alert with shorter refractory periods for alerts that concern subject safety. If the subject does not appropriately respond to the alert in the allotted timeframe, the alert will push to the study coordinator and the on-call investigator according to Appendix M. At that time, the coordinator will pull up the web-based monitoring system. For safety, the Nexus 5 phone will track the subject's location and push GPS coordinates to the cloud server approximately every 10 minutes. Cloud coordinates will be pushed with a known, fixed offset to allow for scrambling.

In order to push alerts to study coordinators and study investigators, the cloud server used for remote monitoring will have a drop down menu for study staff to sign in and out for the duration of their monitoring shift. Each study coordinator and investigator listed in the menu will have a cell phone number on file that can receive texts with pushed alerts.

During all studies, sensed glucose data will be wirelessly transmitted via BTLE from the Dexcom G5 transmitter to the FMPD algorithm every five minutes. The FMPD will calculate insulin doses and will run on a Google Nexus 5 phone. The smart phone will wirelessly

communicate via BTLE to a t:slim insulin pump for automated insulin delivery. For subject safety, if BTLE communication between the phone and insulin pump is disrupted for more than 20 minutes, the system will revert to basal insulin delivery for a pre-set basal profile(s) inputted for the subject at the study start until Bluetooth connectivity is restored. When communication with the pump is restored, the system will automatically resume, updating the IOB accordingly.

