Risks: The risks of the protocol procedures are considered minor. Nonetheless, since pumps and sensors used within automated glucose control systems are imperfect, there is a risk for hyperglycemia and hypoglycemia. Venous blood glucose will be sampled every 15 minutes during the study. The closed-loop system will issue alerts and will be remote monitored during each visit with unserviced alerts being pushed to the study coordinator and investigator. If sensed glucose goes below 70 mg/dl or above 300 mg/dl for these studies, a venous blood glucose check will be required. A research nurse will be present at all times. A study investigator will be on call at all times.

Rarely, there can be allergic responses to insulin such as skin redness, hives, itching of the skin, swelling of the mouth, or breathing difficulties. These reactions are considered very unlikely.

There is a small risk of Dexcom G5 sensor fracture, and in such a case, a piece of the sensor could be left in the tissue after sensor removal. For this reason, the study investigator will inspect each removed sensor for the possibility of breakage or fracture. Any evidence of sensor breakage will be recorded and reported to FDA and the sensor company.

There is a small risk of infection at the insertion sites. This will be minimized by proper sterilization of the device and the subject's skin.

Investigational PDT glucose sensing cannula:

There is a small risk of material from the PDT glucose sensing being left in the body. This risk will be minimized by manufacturing controls to ensure that materials are properly adhered and sensors are slowly withdrawn from the subject. Mild to moderate, short-lived pain from sensor insertion is likely. This will be minimized by using a cannula with minimal diameter and injection depth.

There is a small chance that the needle from the blood draw at the screening visit will cause bleeding, a bruise, an infection or fainting.

There is a small chance that the IV catheter will get an infection and cause swelling, redness and pain. Rarely, an IV catheter can cause a serious infection in the blood or heart valves.

Benefits: The subject may not directly benefit from being in this study; however, their participation may help to advance automated insulin and glucagon delivery technology.

COSTS:

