Appendix B: Alert Manager Specifications

Alarm #	Description of Alarm	When Alarm is Considered Serviced	Instructions for Subject	Alarm Refractory Period (minutes)	Alarm pushed to Study Coordinator	Alarm pushed to Study Investigator
2	ARD \geq 35% for BG \geq 75	Calibration detected	Sensor inaccuracy has been detected, please calibrate sensors with most recent blood glucose value.	30	If refractory period expires	If refractory period expires two or more times in a row
4	CBG \leq 40 mg/dl	NA	CBG is low. Please treat with 30 g of carbs and recheck CBG in 15 minutes.	NA	instantly	instantly
5	CBG < 70 mg/dl and Alert 4 is not active	Rescue carb treatment identified	Blood glucose less than 70 mg/dL, treat with 15-20 g of carbohydrate and recheck in 15 minutes.	30	If refractory period expires	If refractory period expires two or more times in a row
6	Sensor < 70 mg/dl without exercise detection and < 85 mg/dl with exercise detection and no BG given within 15 minutes and alert 5 inactive	Blood glucose value is entered	Sensor is less than 70 mg/dL. Please check blood glucose.	30	If refractory period expires	If refractory period expires two or more times in a row
7	CBG >300 mg/dl	NA	CBG is greater than 300 mg/dl. Please	NA	instantly	instantly

			change the insulin infusion and check your ketones.			
8	Sensor glucose \geq 300 mg/dl and no BG given within 30 minutes and alert 7 inactive	Blood glucose value is entered	Sensor glucose is greater than 300 mg/dl, please check and enter blood glucose, and check insulin pump for malfunctions	30	If refractory period expires	If refractory period expires two or more times in a row
9	Insulin pump communication issue	Autoservices if pump communication is restored	Insulin pump communication issue, please check pump and contact study physician	60 minute initial fire, 20 minute refractory	If refractory period expires during daytime hour of 07:00-22:59 (no nighttime escalation 23:00-06:59)	If refractory period expires two or more times in a row during daytime hour of 07:00-22:59 (no nighttime escalation 23:00-06:59)
10	Insulin meal bolus failure	Clears itself either after the meal flag is older than backlog of 15 minutes or there is not a backlog of insulin to deliver	Insulin meal bolus failed to deliver, please contact the study physician.	20	If refractory period expires	Coordinator will call subject and determine issue and consult with investigator to determine if subject should give bolus open loop.

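### On its plainest reading, alarm 10 (insulin meal bolus failure) clears at 15 minutes, before or just as its 20-minute push to the coordinator falls due

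*Combined protocol and SAP*

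**What the plan says.** In Appendix B, the alarm 10 row sets these terms:

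- **Serviced when:** "Clears itself either after the meal flag is older than backlog of 15 minutes or there is not a backlog of insulin to deliver".
- **Refractory period:** 20 minutes.
- **Coordinator push:** only when the refractory period runs out.
- **Investigator column:** "Coordinator will call subject and determine issue and consult with investigator to determine if subject should give bolus open loop". No timing is attached to this step.
- **On-screen message:** the subject is told that the bolus failed and to contact the study physician.

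Three places in the body text bear on how servicing and pushing relate:

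- The section on the 12 hour Treatment Visit says "Each alert has a specific condition to be met for it to be considered serviced", and then "If the subject does not appropriately respond to the alert in the allotted timeframe, the alert will push to the study coordinator".
- Risks and Benefits describes "unserviced alerts being pushed to the study coordinator and investigator".
- The Protocol Summary says the alerts to be pushed are those the subject has not serviced.

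The Protocol Summary and the treatment-visit section refer to an Appendix M for the push rules. I take this to be the table printed as Appendix B.

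**The concern.** The row appears to defeat its own escalation. Its clearing rule joins two conditions with *either*, so flag age alone suffices and the insulin may still be undelivered. If a serviced alarm is no longer pushed, an alarm cleared at 15 minutes has nothing left to push at 20.

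The row plainly intends that the coordinator and investigator decide whether a failed meal bolus should be given open loop. Alarm 10 is the only alarm in the table specific to that failure. Meals are planned at 80 to 150 g of carbohydrate, so a missed bolus matters for glucose control on the day. What may be lost is the automatic text to staff. The on-screen alert to the subject still fires.

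The other automatic routes are slower or do not restore the bolus. If lost pump communication caused the failure, alarm 9 has a "60 minute initial fire, 20 minute refractory". The 20-minute fallback in the treatment-visit section restores the pre-set basal profile only.

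**Working it through.** The plan gives no figure to reproduce, so the check is a timeline and a count.

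**Inputs**

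- Flag-age limit 15 minutes and refractory period 20 minutes (Appendix B, alarm 10).
- Ten subjects (Study Population) and two meals per visit (12 hour Treatment Visit).
- Assumption: the meal flag is set at *t* = 0 and the alarm fires at *f*, with 0 ≤ *f* ≤ 15 minutes. The documents do not give *f*.
- Assumption: the refractory clock starts when the alarm fires.
- Assumption for one variant: alerts are checked every 5 minutes. The documents give that interval for sensor data, sent "from the Dexcom G5 transmitter to the FMPD algorithm every five minutes", and not for alert checks.

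**Gap between clearing and push**

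The push is due at *f* + 20. In continuous time the alarm clears at 15, so the gap is (*f* + 20) − 15 = *f* + 5.

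| *f* (min) | Clears | Push due | Gap |
|---|---|---|---|
| 0 | 15 | 20 | 5 |
| 5 | 15 | 25 | 10 |
| 10 | 15 | 30 | 15 |
| 15 | 15 | 35 | 20 |

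Variants:

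- **5-minute check cycle, flag strictly older than 15:** with checks at 0, 5, 10 and so on, the alarm clears at 20. The gap runs from 20 − 20 = 0 (*f* = 0, a tie) to 35 − 20 = 15. Shifting the phase of the checks keeps the gap within 0 to 15.
- **15 minutes counted from firing:** clears at *f* + 15, so the gap is always 5 minutes in continuous time.
- **Refractory clock started at the meal flag:** 20 − 15 = 5 minutes in continuous time, and as little as 0 on the 5-minute cycle.
- **Clearing does not cancel the clock:** the push still goes out, at *f* + 20 = 20 to 35 minutes after the flag, when the flag has already lapsed.

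In none of these variants is the push due before the alarm clears.

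**Is alarm 10 unusual?**

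Sixteen alarms go to the coordinator on expiry of a refractory period: 2, 5, 6, 8, 9, 10, 11, 12, 13, 14, 17, 19, 21, 22, 23 and 24. Three concern glucagon (11, 22, 24) and one is the 72-hour insulin change (23); none of these applies to a 12-hour insulin-only visit. That leaves 16 − 4 = 12. Eleven of the 12 need an action or a restored function: a glucose entry, a calibration, a carbohydrate treatment, a restored connection or, for alarm 21, a successful bolus. Only alarm 10 can be serviced by elapsed time with its fault unresolved.

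**Exposure**

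Planned meal boluses: 10 × 2 = 20, excluding repeated visits. The documents give no bolus failure rate, so no number of affected meals can be stated.

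**The case against.** The strongest reply is that the timing conflict rests on premises the documents do not state.

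- **The clearing clause is garbled.** It speaks of a flag older than a backlog of 15 minutes. If clearing depended on the age of the backlog itself, the alarm might still be open when the push falls due. This stands, and it makes every minute figure conditional on the plainest reading.
- **No text says that clearing cancels the refractory clock, or when that clock starts.** Only alarms 9 and 11 separate a first firing from the refractory period. Alarm 26 is pushed at once and then auto-clears, yet carries a 60-minute refractory period, so in at least one row that period is not simply the time allowed for servicing. The Protocol Summary and the treatment-visit section tie the push to what the subject does, and self-clearing is not a subject response. This leaves room for a late push. Against it, the general rule that each alert has its own serviced condition, the Risks and Benefits wording, and the rows that service themselves once the fault is resolved (9, 17, 19, 21) favour the reading that a serviced alarm is not pushed.
- **The coordinator's call has no stated timing.** It sits in the investigator column, so its dependence on the push is an inference. This stands too.
- **The text goes to people already there.** The treatment-visit section says "A study coordinator will be present once the closed loop study begins to run the YSI analyzer", with cloud monitoring. A coordinator or nurse stays with the subject, trained staff help with each meal entry, glucose is measured every 15 minutes, and a capillary glucose above 300 mg/dl (alarm 7) is pushed instantly to both staff roles. This keeps the consequence small but does not remove the conflict within the row.

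A reader might go further and infer that the plan certainly suppresses this escalation, or that failed meal boluses would go unnoticed. The documents support neither: the first depends on unstated clock rules, and the second ignores the on-screen alert and the staff present.

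**Conclusion.** The point holds as a conditional one. On the plainest reading, alarm 10 is serviced by flag age before its coordinator push is due, or at the same moment, so the push would probably not occur. This rests on the 15 minutes being counted from the meal flag or from firing, on firing within 15 minutes of the flag, and on a serviced alarm not being pushed. If the last assumption fails, the push is late rather than lost.

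Severity is minor and confidence medium. It touches one of 12 relevant alarms and at most 20 planned meal boluses. No quantified harm is claimed, and no effect on the comparison of sensor accuracy between lispro and saline. It is worth correcting because the row's stated intent is a staff decision on dosing and the correction is cheap.

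**What to change.** Push alarm 10 to the coordinator when it fires. Alarm 15, which has a similar call-and-consult step, is already pushed instantly. At the latest, push it when the meal flag expires with a backlog outstanding. Do not treat flag age alone as servicing. Reword the clearing clause, and state when the refractory clock starts and whether self-clearing cancels it. The dosing decision stays with the investigator.

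The cost is at most 10 × 2 = 20 extra texts to on-site staff if every planned meal bolus failed once, plus a change to the controller's alert logic whose effort the documents do not state.

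If the software cannot readily be changed, instruct the on-site coordinator in writing to act on the on-screen alarm without waiting for a push. That largely restates the row; what it adds is that the call does not depend on the text.

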Appendix C: PDT Glucose Sensing Cannula Device Description

The Pacific Diabetes Technologies device is able to measure interstitial glucose at the same site of insulin delivery (insulin is delivered via a separate pump that is not a part of this device). Success will be measured by how well the sensor tracks blood glucose changes without being affected by the preservatives in insulin.

PDT's CGM insulin infusion system is composed of four distinct components that function together to meet the intended use of the device. Images of the various components are included in the appendix. The parts are as follows:

Component	Purpose
Sensing Cannula and Housing	The Sensing Cannula sits in subcutaneous interstitial fluid to provide measurement of glucose to an externally worn sensor Housing.
Electronic Module	Attaches to the Sensing Cannula and Housing and stores and transmits a glucose signal to an external location
Insulin Infusion Set	Connects the PDT Sensing Cannula to the separate insulin pump
Insertion Device	Allows accurate and simple insertion of the device into its proper location.

Manufacturing Information: The investigational sensing cannulas/housings and electronic modules are manufactured at PDT's laboratories. All manufacturing and testing is performed in a cleanroom or laminar flow hood. Numerous tests are conducted on all manufactured sensors, throughout the fabrication process, to verify sensor functionality.

Sterilization: The investigational devices have been sterilized by a validated method (electron beam, dose=26 kiloGray). Each sterile study device is packaged in a 50 mL plastic vial (with screw cap) within a cardboard UPS mailing envelope.

Storage Conditions: Sterile sensing cannulas are stored at room temperature, and are not removed from the 50 mL capped plastic tubes before use. A clear adhesive seal, applied between the side of the cap and the side of the tube, safeguards that the tube remains tightly sealed.

Product Labeling: Shown here is a sample of the product labeling that will be displayed on the investigational CGM insulin infusion set. Note that this product label includes the statement “Caution–Investigational Device. Limited by Federal (or United States) Law to Investigational Use.” Note that the label also states “Do not use if package is damaged, or if the seal is broken or missing” (not shown in picture).

Device Insertion Steps UPDATE for Tslim

NOTE -- the non-sterile devices indicated below will be sanitized with SaniCloth AF-3 wipes prior to use.

Prepare Devices

Physician dons gloves and prepares a sterile field. She carries out the steps listed below.

1. Remove from the sterile 50 mL vial the CGM insulin infusion set. Separate the insulin infusion tubing (Panel 1) from the sensor housing (Panel 2) by pressing the outer arms of the quick connector (Panel 1). Place the insulin infusion tubing on sterile field.
2. Place the sensor housing on the non-sterile loading base being careful to avoid contaminating the sterile cannula.
3. Place the non-sterile insertion device (Panel 5) over the loading base and press down. This action loads the sensor housing into the insertion device.
4. Cock the insertion device and set it aside for later use. Set aside the loading base for later use.

Insert cannula

5. Prepare the skin site with isopropyl alcohol pad(s) in ever-widening circles.
6. Remove the upper and lower liners from the non-woven adhesive patch.
7. Place the non-woven bandage on to the skin surface so that the skin worn device is oriented horizontally (left-right) on the body, not vertically.
8. Align the loaded inserter on to the non-woven bandage, then activate the inserter (insert cannula through skin). Visually verify that the cannula is in the tissue.
9. Remove the inserter and set aside

[figure not shown]
Insert and Anchor Electronic Module

10. Remove the electronic module (Panel 7) from the charger (Panel 6).
11. Using the laptop program, verify connectivity to the Bluetooth electronic module, then connect the electronic module to the sensor housing as shown in Panel 4. The electronic module will automatically start transmitting repeated “Active Status” signals to the laptop computer.
12. Apply polyurethane overbandage (such as Tegaderm), being careful to leave space for mating of quick connector to sensor housing.

Attach Insulin Pump and Fill the Insulin Fluid Path (Prime)

13. Connect reservoir to Tandem t:slim insulin pump. Avoid touching the sterile recessed reservoir-connection needle.
14. Using the pump interface, prime insulin line until insulin liquid is seen dripping through needle on quick connector. Avoid touching the sterile recessed quick connector needle.
15. Attach the quick connector to the sensor housing.
16. Using the pump interface, carry out the needle prime (0.7 units) to fill the cannula with insulin.
17. Now the insulin delivery rates can be programmed and initiated.

COMPONENTS OF CGM/INSULIN INFUSION SYSTEM

APPENDIX D: TOLERABILITY QUESTIONNAIRE

APPROXIMATELY 15 MINUTES AFTER INSERTION

1. Did you have any discomfort WHILE THE DEVICES WERE BEING INSERTED?

LEFT

- No discomfort → **Go to Question #3**
- Mild discomfort
- Moderate discomfort
- Severe discomfort

RIGHT

- No discomfort → **Go to Question #3**
- Mild discomfort
- Moderate discomfort
- Severe discomfort

2. The discomfort from the insertion LASTED how long?

LEFT

- Less than 10 seconds
- 10 seconds to 1 minute
- 1 to 5 minutes
- Longer than 5 minutes

RIGHT

- Less than 10 seconds
- 10 seconds to 1 minute
- 1 to 5 minutes
- Longer than 5 minute

3. Did you have any discomfort that started AFTER insertion?

LEFT

- No discomfort → **Stop here. Don't answer Question #4**
- Mild discomfort
- Moderate discomfort
- Severe discomfort

RIGHT

- No discomfort → **Stop here. Don't answer Question #4**
- Mild discomfort
- Moderate discomfort
- Severe discomfort

4. The discomfort that started AFTER insertion LASTED how long?

If you currently feel discomfort, please mark "I still feel discomfort"

LEFT

- Less than 10 seconds
- 10 seconds to 1 minute
- 1 to 5 minutes
- Longer than 5 minutes
- I still feel discomfort

RIGHT

- Less than 10 seconds
- 10 seconds to 1 minute
- 1 to 5 minutes
- Longer than 5 minutes
- I still feel discomfort

APPROXIMATELY 2 HOURS AFTER INSERTION

1. Did you have any discomfort AFTER the first 15 minutes?

LEFT

- No discomfort → **Stop here. Don't answer Questions #2 and #3**
- Mild discomfort
- Moderate discomfort
- Severe discomfort

RIGHT

- No discomfort → **Stop here. Don't answer Question #2 and #3**
- Mild discomfort
- Moderate discomfort
- Severe discomfort

2. How would you describe the discomfort?

LEFT

- Pain (e.g., stinging)
- Itching (e.g., burning)
- Other, please describe:

RIGHT

- Pain (e.g., stinging)
- Itching (e.g., burning)
- Other, please describe:

3. The discomfort LASTED how long?

LEFT

- 30 seconds or less
- More than 30 seconds but less than 5 minutes
- 5 to 20 minutes
- More than 20 minutes but less than 1 hour
- 1 hour or more
- I still feel discomfort

RIGHT

- 30 seconds or less
- More than 30 seconds but less than 5 minutes
- 5 to 20 minutes
- More than 20 minutes but less than 1 hour
- 1 hour or more
- I still feel discomfort

END OF STUDY

OVERALL, did you have any discomfort after the devices were inserted? Please don't include discomfort experienced during the insertion. You can mark as many circles as necessary – For example, from a single device (left or right), you may have felt mild discomfort during part of the study, and moderate discomfort during another part of the study.

LEFT

NO DISCOMFORT

MILD DISCOMFORT

How would you describe the discomfort?

- Pain (e.g., stinging) Itching (e.g., burning)
 Other:

How long did it last?

- 1 minute or less
 More than 1 minute but less than 10 minutes
 10 minutes to 1 hour
 More than 1 hour but less than 5 hours
 5 hours or more

MODERATE DISCOMFORT

How would you describe the discomfort?

- Pain (e.g., stinging) Itching (e.g., burning)
 Other:

How long did it last?

- 1 minute or less
 More than 1 minute but less than 10 minutes
 10 minutes to 1 hour
 More than 1 hour but less than 5 hours
 5 hours or more

SEVERE DISCOMFORT

How would you describe the discomfort?

- Pain (e.g., stinging) Itching (e.g., burning)
 Other:

How long did it last?

- 1 minute or less
 More than 1 minute but less than 10 minutes
 10 minutes to 1 hour
 More than 1 hour but less than 5 hours
 5 hours or more

RIGHT

NO DISCOMFORT

MILD DISCOMFORT

How would you describe the discomfort?

- Pain (e.g., stinging) Itching (e.g., burning)
 Other:

How long did it last?

- 1 minute or less
 More than 1 minute but less than 10 minutes
 10 minutes to 1 hour
 More than 1 hour but less than 5 hours
 5 hours or more

MODERATE DISCOMFORT

How would you describe the discomfort?

- Pain (e.g., stinging) Itching (e.g., burning)
 Other:

How long did it last?

- 1 minute or less
 More than 1 minute but less than 10 minutes
 10 minutes to 1 hour
 More than 1 hour but less than 5 hours
 5 hours or more

SEVERE DISCOMFORT

How would you describe the discomfort?

- Pain (e.g., stinging) Itching (e.g., burning)
 Other:

How long did it last?

- 1 minute or less
 More than 1 minute but less than 10 minutes
 10 minutes to 1 hour
 More than 1 hour but less than 5 hours
 5 hours or more

